4.3 Study Enrollment Procedures

Identifying survey participants

The PI has already established a strong network with the Bhutanese community and completed her needs assessment studies collecting determinants of a mental health problem through engaging community members in the research process. We will use an existing community network to spread the study information in coordination with church leaders, community research assistants (RAs), and supervisors. PI will prepare an oral script including study objectives, eligibility criteria, intervention procedure, study and survey information, hair sample collection, and informed consent procedure. It will also distribute it to them to spread the study information. They will be requested to disseminate the information about the study purpose and process to their community in phone or in-person meetings in any of their gatherings, word of mouth, formal/informal discussions, and festivals to check-in for their interest to participate in the study. Interested participants will be requested to contact PI, RAs, and supervisors.

Recruiting survey participants

Community RAs from the local area will be mobilized to reach interested families to check their eligibility and make a list of eligible participants. Eligibility criteria for participants are: being Bhutanese adults 18 years or older resettled in Massachusetts with a score of 14 or below on the Patient Health Questionnaire-9, showing commitment to complete the intervention procedure, and giving informed consent to participate in the study. RAs will recruit interested eligible participants with their informed consent and will conduct a baseline survey. RAs will be asked to leave a note in the screening tool and screening log of reasons for ineligibility, such as a PHQ-9 score of more than 14 or any history of clinically diagnosed mental health problems or taking any medication related to mental health problems. RAs will also leave a note for non-participation of eligible candidates in the screening tool and screening log.

Randomizing study participants for intervention and control

We will randomly allocate selected families into intervention and control groups using a random sampling method after the baseline survey. We will randomly assign 116 interested

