families (58 families per intervention and control) using a random number table. For random allocation, first, PI will prepare the sampling frame that lists interested families. Second, assign a number to each family in the sampling frame. Third, select 116 numbers using a table of random numbers. PI will request any interested community member to point one number in the random number table by closing his/her eyes. Since the selected families total 116, or three digits, we will choose only the first three digits of the number chosen as the first sampled family. Finally, we will choose other numbers moving down the first number column until all 116 families will be selected.

We will assign a random number selected at the first attempt for intervention and the second attempt for control. It means random numbers selected at odd attempts (first, third, seventh,) will be assigned for intervention and at even attempts (second, fourth, sixth...) for control. The sample elements corresponding to the selected random numbers become the sample. Procedures are in place for tracking the participants for intervention and follow-up (e.g., contact address and phone). RAs will visit selected families and brief them about study procedures, informed consent, and procedures to protect human subjects. All adult members of selected families who meet the inclusion criteria and give informed consent will be recruited for the study. We will follow up with all families randomized to either study arm. We will not follow up with participants if they decide to end their participation at a particular time point of our study. But, we will include their already collected data in our analysis. Given our strong community networks and mobilization of community RAs, we anticipate low attrition rates in practice. Ethical approval for our study will be obtained from the Institutional Review Board at UMass Amherst.

Recruitment of focus group discussion participants

PI will collect data on engagement, acceptability, and satisfaction of intervention delivery by conducting focus group discussions (FGD) with selected interested participants who are already enrolled in our study from the intervention group (30) upon intervention completion using a brief guide questionnaire. The participant will be eligible to attend the focus group discussion if they are already enrolled in our intervention group and have attended our mental health promotion program. RAs will inform participants about FGD

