6.2 Description of Evaluations

6.2.1 Screening Evaluation

These evaluations occur to determine if the participant is eligible for the study.

Consenting Procedure

Trained RAs will meet interested participants and inform them about screening and study procedures to each participant using UMass Amherst IRB-approved single informed consent form. A copy of the informed consent form will be provided to each participant for their review. If they want, RAs can read informed consent for them. Participants will be given enough time to review informed consent and ask questions if they have any confusion. RAs will ensure that participants understand screening, study procedure, privacy and confidentiality of private information, and NDA data sharing policy. They will be reminded that their participation in the study is voluntary and free to leave the study without penalty. Once participants understand about study details, RAs will request them to do their signature or write their initials or fingerprint for those who cannot write their names in the two copies of the informed consent form before collecting their information. One copy of the signed informed consent form will be provided to each participant. We will not recruit any individuals who are unable to consent for themselves. The signed informed consent form will be stored securely in the locked cabinet of the PI's office. (Please find attached informed consent for details)

Screening

RAs will screen interested participants after obtaining their informed consent on the same day. We plan to include eligible Bhutanese adults aged 18 or older interested in participating in the study as primary study participants. This includes parents and their adult children aged 18 and above. At baseline, we will use our screening tool to identify individuals without significant depressive symptoms, as we aim to evaluate the effect of our intervention to prevent depression rather than treat depression. Eligibility criteria for our primary study participants include Bhutanese adults 18 years or older (both parents and children of each family) resettled in Massachusetts with a score of 14 or below on the Patient Health Questionnaire (PHQ-9), a screening

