6.2.2 Enrollment, Baseline, and Randomization

Enrollment

In this study, the enrollment date is the day the participant has met all the screening criteria and signs a single informed consent form that describes both screening and study procedures. RAs will record the enrollment date on a case report form along with the allowable window between screening and randomization.

Baseline Assessments

For participants who will have successfully been screened for eligibility and are enrolled in the study, baseline assessments will be performed to measure the study outcome on the same day of enrollment. We will measure study outcomes as listed below:

Anxiety and Depressive Symptoms

The Hopkins Symptom Checklist-25 (HSCL-25)² will be used to measure anxiety and depressive symptoms² experienced over the past month. It is composed of a 10-item subscale for anxiety and a 15-item subscale for depression, with each item scored on a Likert scale from 1 (not at all) to 4 (extremely). The scale was validated for use in Nepal with a clinical DSM-IV diagnosis of major depressive disorder. The sensitivity and specificity with a cutoff point of 1.75 were 0.87 and 0.60, respectively, with an area under the curve of 0.79.⁵⁰ The HSCL-25 has widely been used in studies among refugees in other countries as well as Nepal. The HSCL-25 score was categorized into two groups: the cutoff score of 1.75, depressed (1.75 or more), and not depressed (below 1.75). The scale has high internal consistency for anxiety (Cronbach's $\alpha = 0.92$) and depression (Cronbach's $\alpha = 0.94$) in our previous Bhutanese study.³⁹

Perceived Stress

The 10-item Cohen Perceived Stress Scale (PSS)¹ will be used to assess perceived stress. The PSS uses a 5-point Likert scale (ranging from 0, “never” to 4, “very often”) to assess psychological stress experienced during the past month, including

the extent to which situations felt unpredictable, uncomfortable, and overwhelming. The items included in the PSS scale are easy to understand as it was designed for use with community samples with junior high school education. This scale has been widely used in different populations, including immigrants. The scale has high internal consistency (Cronbach's $\alpha = 0.80$) in our previous Bhutanese study.³⁹ Items were summed to provide a total score with higher scores indicating greater perceived stress.

Physiological stress

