Family satisfaction: Family satisfaction with various aspects of family functioning, including family closeness, flexibility, and communication will be measured using a 10-item family satisfaction scale.⁶⁰ A sample item from this scale is, “How satisfied are you with the degree of closeness between your family members.” Participants will be asked to respond on a 5-point Likert-type scale, ranging from *very dissatisfied (1)* to *extremely satisfied (5)*.

Randomization

Participants will be randomly assigned to intervention and control groups within 7-days of baseline survey completion. The first session of intervention will be delivered to the intervention and control groups within the seven days of baseline survey completion.

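### Section 4.3 gives two orders for enrolling adults and allocating families; the text that places the draw first should be reworded so that enrolment cannot depend on arm

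*Combined protocol and SAP*

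**What the plan says.** Section 4.3 of the combined protocol and SAP has research assistants (RAs) check eligibility, obtain consent and carry out the baseline survey. Its randomisation text then opens: "We will randomly allocate selected families into intervention and control groups using a random sampling method after the baseline survey". Section 6 gives the same order. On screening: "RAs will screen interested participants after obtaining their informed consent on the same day". On baseline: "baseline assessments will be performed to measure the study outcome on the same day of enrollment". On allocation: "Participants will be randomly assigned to intervention and control groups within 7-days of baseline survey completion". Deviation code 14 in Section 10.2.5 treats randomising someone before eligibility is known as a deviation.

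The same randomisation text in Section 4.3 then describes the draw. It begins "PI will prepare the sampling frame that lists interested families". A total of 116 numbers are taken from a random number table, with odd attempts going to intervention and even attempts to control. After that come two sentences: "RAs will visit selected families and brief them about study procedures, informed consent, and procedures to protect human subjects" and "All adult members of selected families who meet the inclusion criteria and give informed consent will be recruited for the study".

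Masking is stated as none (Section 3), and no concealment step is described.

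**The concern.** The two parts of Section 4.3 do not describe the same sequence. In the first, the adults are enrolled and measured before their family has an arm. In the second, one draw both picks the family and fixes its arm, and briefing on consent, eligibility and recruitment are described afterwards.

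The order matters because families are randomised but adults supply the data. If adults choose to join once the arm is set, who joins can depend on the arm. The two programmes ask for different amounts of time (Section 5.1): 900 minutes for PMP-I, against 300 minutes for the talk programme plus 240 minutes of mental health sessions afterwards, so 540 in total. Baseline might also no longer precede randomisation.

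The analysis in Section 9.2 would not reliably correct such a difference. Baseline is one of the repeated outcomes in the three-level model and time is centred at the endpoint. The key contrast γ001 is therefore not baseline-adjusted unless the covariate rule, which adds variables that differ significantly between arms, happens to bring the variable in.

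**Working it through.** **The two sequences side by side**

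| Step | Opening of the randomisation text in 4.3, with 6.2.1 and 6.2.2 | Description of the draw in 4.3 |
|---|---|---|
| 1 | Consent, then screening the same day | List interested families |
| 2 | Baseline on the day of enrolment | Draw 116 families; odd or even attempt sets the arm |
| 3 | Allocate families, within 7 days of baseline | Brief the drawn families on procedures and consent |
| 4 | First session | Recruit adults who meet the criteria and consent |

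Two features make the right-hand column more than a stray phrase. There, a family counts as selected because its number was drawn. And adults who had already consented and been surveyed would not need briefing on consent, or recruiting if eligible. Against that, the opening sentence also speaks of selected families before allocation, and the later sentences do not say that they follow the draw.

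**Illustrative size.** The plan gives no figure on this point, so there is nothing to reproduce. The rates below are assumptions.

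Let p be the share of eligible adults who fail to enrol in one arm only, p = .05 or .10.

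- Non-enrollers .5 SD more stressed than enrollers: shift = .5p = .025 or .050 SD.
- Decision correlated .5 with stress: shift = .5·φ(z)/(1−p), which is .5 × .1031/.95 = .054 or .5 × .1755/.90 = .097 SD.

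Against the target ES of .30 (Section 9.1), .025/.30 = 8% and .097/.30 = 32%.

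Standard error of the difference, with ICC .10 and 58 families per arm (Section 9.1): √(2/n) × √(1 + (m−1) × .10), where n is adults per arm and m is adults per family.

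- 226 adults (Sample Size and Population): n = 113, m = 226/116 = 1.95; .133 × √1.095 = .139.
- 3 per family, the middle of the stated 2–4: n = 174; .107 × √1.2 = .117.

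Two-sided error rate of γ001 when there is no true effect, approximated by a simple endpoint comparison, is Φ(−1.96 + shift/SE) + Φ(−1.96 − shift/SE). The chance that the Section 9.2 baseline t-test flags the variable uses the unclustered SE (.133 or .107) for the cut-off and the clustered SE for the true spread.

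| Shift (SD) | Error rate, shift fully persists (226 / 348 adults) | Error rate, half persists | Baseline t-test flags it |
|---|---|---|---|
| 0 | .050 / .050 | .050 / .050 | .061 / .074 |
| .025 | .054 / .055 | .051 / .051 | .065 / .080 |
| .05 | .065 / .071 | .054 / .055 | .078 / .100 |
| .10 | .111 / .136 | .065 / .071 | .129 / .178 |

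The t-test would miss even the largest of these shifts in more than 80% of trials.

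**The case against.** The strongest reply is that the intent is plain and only the drafting is loose. The randomisation text opens with allocation after baseline, which can be read as governing the rest. Its numbered steps cover only the draw. The sentences around the recruitment text run through tracking, follow-up and attrition and end with ethics approval still to be obtained, so their order cannot be chronological. Section 6 gives a dated operational sequence that consistently puts enrolment before allocation. All of this stands. It is why a reader who infers that the trial plans to recruit after allocation would go beyond the documents.

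A reader might also infer that the order could not be checked afterwards. That too is stronger than the text supports. The Section 6.1 form has separate dated entries for consent, screening, eligibility and the baseline measures. Section 6.2.2 adds: "RAs will record the enrollment date on a case report form along with the allowable window between screening and randomization". Section 4.3 has RAs note why eligible people did not take part. RA training, monitoring by the principal investigator and deviation codes 13 to 15 also apply. The gap is narrower: on the Section 6.1 form, enrolment and randomisation share one row.

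Finally, the size is hypothetical, and a fully persistent shift would cancel in the change contrast γ101. This is fair, but Section 9.2 names γ001 as the key test and says that the study is not powered for change.

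What remains is that a document describing itself as a manual of operations (Section 10.2.3) contains two orders, and one of them, taken literally, is unsafe.

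**Conclusion.** The inconsistency is real and should be removed. Consent, screening and baseline before allocation is very probably the intended order, and if it is followed this bias does not arise. The documents do not show that enrolment will depend on arm.

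If the description of the draw were followed literally, arm-dependent enrolment would be possible and γ001 could be biased in either direction. The amount cannot be calculated from the documents. With an assumed 5–10% one-arm non-enrolment, the shift is about .03–.10 SD. Most of the scenarios leave the nominal 5% error rate at 5–7%; reaching 11–14% needs the largest shift and full persistence to the endpoint. Those figures rest wholly on the assumed non-enrolment rates, the .5 SD gap or .5 correlation, and the degree of persistence. They show why the order is worth protecting and are not a forecast.

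**What to change.** 1. In Section 4.3, define the sampling frame as families whose interested adults have already consented, been screened and completed baseline.
2. Move the sentences on briefing families and recruiting adults ahead of the description of the draw.
3. State that each family's analysis roster is fixed before its draw. Adults who come forward later may attend sessions but are not in the outcome analysis.
4. Split the shared enrolment and randomisation row of the Section 6.1 form into two, so that the randomisation date is recorded separately.

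The cost is some rewording and one extra form row. The order is the one that Section 4.3 already states at the start of its randomisation text, so sample size and outcomes are unchanged. The downside is that a few late-joining adults are left out of the outcome analysis.

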The PI will conduct FGD in the Nepali language with interventionists, supervisors, and participants separately to collect information on barriers and facilitators of intervention, perceptions about whether the intervention met participants' needs, and feedback on how effectively the program team worked with participants. Interviews and FGD will be documented verbatim in a written transcript for subsequent analysis. All qualitative data will be analyzed using thematic content analysis.⁵³ Feedback provided by the field staff will be reviewed and coded to identify recurrent themes regarding the intervention's acceptability. All analyses will be conducted in Nepali and translated into English. Fidelity data will be used to assess intervention content and transmission. We will determine retention by obtaining proportions of participants attending all or portion of sessions.

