8 INTERVENTION DISCONTINUATION

This study included behavioral intervention, which does not have any noted harm. Even though subjects may withdraw voluntarily from participation in the study at any time and for any reason. Participants should continue to be followed for outcomes, with their permission, even if the study intervention is discontinued. The replacement of subjects will not be made for those who withdraw or discontinue their participation in the study. RAs will collect safety data on any subject discontinued due to adverse events or serious adverse events and will be given appropriate care under medical supervision until the symptoms of any adverse events resolve or the subject's condition becomes stable. If voluntary withdrawal occurs, the subject will be asked to continue scheduled evaluations and complete an end-of-study evaluation. In any case, every effort will be made to undertake protocol-specified safety follow-up procedures.

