content analysis.⁵³ Feedback provided by the field staff will be reviewed and coded to identify recurrent themes regarding the intervention's acceptability. All analyses will be conducted in the Nepali and translated into English. Fidelity data will be used to assess intervention content and transmission. We will determine retention by obtaining proportions of participants attending all or portion of sessions.

Aim 2b Intervention efficacy: We will carry out data management and descriptive analyses for study outcomes. Means, standard deviations, and percentile distributions will be used to describe the continuous baseline variables. Frequencies and percentages will be used to describe categorical variables. We will compare baseline characteristics of intervention and control groups using chi-square and t-tests as appropriate. While differences between groups are not expected because of the randomization used in the study design, variables showing significant differences between the two groups will be included as covariates in primary analyses. We will compare participants' characteristics to follow-up to those with complete data to assess potential limitations in recruitment and retention.

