The primary analyses will test whether participants' outcomes in the PMP-I arm differ from those in the control arm. Multilevel modeling will compare outcomes of each treatment arm while accounting for the clustering of participants within families. Continuous outcomes will be analyzed using hierarchical linear modeling, and dichotomous outcomes will be analyzed using multilevel generalized linear models with a Bernoulli distribution appropriate to nonlinear binary outcomes.⁶⁴ We expect approximately 2-4 members for each of the 58 families in each treatment arm, and the correlation among family members' responses will be accounted for in the model. Hierarchical or multilevel modeling is suited to these data as it accounts for the clustering of members within families and unbalanced designs (i.e., different family sizes).⁶⁴ This will be an intention-to-treat type of analysis, as multilevel modeling allows retention of all participants irrespective of the number of sessions attended (multilevel modeling uses maximum likelihood estimation, one of the recommended ways of handling missing data). The analysis will estimate endpoint outcomes based on repeated measures (Level 1) within individuals (Level 2) within families (Level 3). This three-level model is represented by the following equations:

Level 1: $Outcome_{ijk} = \pi_{0jk} + \pi_{1jk} * Time_{ijk} + e_{ijk}$; Level 2: $\pi_{0jk} = \beta_{00k} + r_{0jk}$; $\pi_{1jk} = \beta_{10k} + r_{1jk}$
 Level 3: $\beta_{00k} = \gamma_{000} + \gamma_{001} * PMP-I_k + u_{00k}$; $\beta_{10k} = \gamma_{100} + \gamma_{101} * PMP-I_k + u_{10k}$

[figure not shown]

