Where the outcome is measured at each repeated measure *i* for each individual *j* within each family *k*. Time is centered at the endpoint, so that β_{00k} estimates the value of the outcome for each family at the end of the study, informed by all data points available for that family. If an endpoint observation is missing due to drop out, the advantage of multilevel modeling is that it utilizes maximum likelihood estimation, which estimates the expected outcome for that cluster using information from prior assessments as well as the expected value from the entire model. The key test of difference in the outcome between the treatment groups is represented by γ_{001} (in bold); this is a test of difference in outcome at endpoint between families randomized to PMP versus not. We expect this test of difference to be statistically significant based on our power analysis for the difference in outcome *level* at the endpoint. Note that this model will also test group differences in *change* in each outcome (γ_{101}). While our pilot is not powered for the significance of effects of change over time, we will be able to obtain estimates of ES for change for use in future larger-scale trials and analyses.

The ultimate goal of our analyses is to estimate the ES for this prevention trial for each outcome, to inform our planning of a full-scale trial. As noted earlier, we have powered this pilot prevention trial with a conservative estimate of effect size based on a similar study in a clinical population, but no known studies have characterized the precise effect size of PMP as a preventive intervention; a goal of our pilot is to estimate the expected effect on the population of interest (i.e. an at-risk vs clinical population). All analyses will be performed using SAS, version 9 (SAS Institute Inc, Cary, NC).

Aim 2c Mediating effects: Separate models will be created to evaluate the relationships between mediators (targets) and outcomes and to explore mediators (e.g. coping) of intervention-outcome relation.

In this aim, we aim to test the potential *mediators* of the treatment-outcome association by conducting mediational analyses in a multilevel regression framework.⁶⁵ Following current

[figure not shown]
Figure 1 Mediational Analysis Framework

recommended best practices in mediational analysis, we will conduct these analyses using recommended practices for mediation with a multilevel framework.⁶⁶⁻⁶⁸

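### Sections 4.3 and 8 give different outcome follow-up rules for people who leave the study, and the Aim 2a retention rate is computed from session attendance, so it cannot register loss at Day 42 or Day 132

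*Combined protocol and SAP*

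**What the plan says.** **Follow-up of people who leave.** In its randomization text, Section 4.3 says that all randomized families will be followed up. It then makes an exception for individuals: "We will not follow up with participants if they decide to end their participation at a particular time point of our study". Their data collected up to that point stay in the analysis.

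Section 8 starts from the same event: "subjects may withdraw voluntarily from participation in the study at any time and for any reason". Its rule is different: "If voluntary withdrawal occurs, the subject will be asked to continue scheduled evaluations and complete an end-of-study evaluation". It also covers people who stop only the intervention: "Participants should continue to be followed for outcomes, with their permission, even if the study intervention is discontinued".

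**Retention.** Aim 2a (Section 1.2) lists session attendance and retention as two separate rates. The only formula for retention stands in Section 5.2 and is repeated in Section 9.2 under Aim 2a: "We will determine retention by obtaining proportions of participants attending all or portion of sessions". Elsewhere in Section 9.2 the word means other things. Under Aim 2b, participants are compared with those "with complete data to assess potential limitations in recruitment and retention". The primary-analysis text says that "multilevel modeling allows retention of all participants irrespective of the number of sessions attended".

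**Missing endpoints.** When the endpoint is missing through dropout, Section 9.2 relies on maximum likelihood, which "estimates the expected outcome for that cluster using information from prior assessments as well as the expected value from the entire model".

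**The concern.** There are two independent problems.

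First, field staff have two instructions for the same person. If a participant refuses all further contact, both sections lead to the same result. If a participant leaves the study but would agree to be assessed, Section 8 has someone ask and Section 4.3 does not. The key test in Section 9.2 is the arm difference at the end of the study. Following Section 4.3 therefore gives up endpoint outcomes that might have been collected and leaves the comparison resting on a missing-at-random assumption. People who only miss sessions are not affected, because they have not left the study.

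Second, a feasibility trial has to tell the planners of the next trial what proportion of participants complete the outcome assessments. The retention statistic defined here repeats attendance and stops before the outcome assessments begin.

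**Working it through.** **1. Schedule** (Section 3; Section 6.1 grid; Sections 6.2.3 and 6.2.4). Sessions 1 to 5 fall on Days 7, 14, 21, 28 and 35. Stress, anxiety and depression are measured at Days 0, 42 and 132, which is 3 occasions. Hair is sampled at Days 0 and 132, which is 2 occasions.

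**2. What each follow-up rule yields for a leaver who would accept assessment**

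| Time of leaving | Section 4.3: psychological | Section 4.3: hair | Section 8, if the person agrees |
|---|---|---|---|
| Days 7–35 | 1 of 3 (nothing after randomization) | 1 of 2 | up to 3 of 3 and 2 of 2 |
| After Day 42, before Day 132 | 2 of 3 (endpoint missing) | 1 of 2 | up to 3 of 3 and 2 of 2 |

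There is no Day 42 hair sample, so under Section 4.3 anyone leaving before Day 132 has baseline cortisol only.

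**3. Whether session-based retention can detect loss.** The last attendance point is Day 35. That is 42 − 35 = 7 days before the first post-baseline assessment and 132 − 35 = 97 days before the last.

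| Sessions attended | Post-baseline assessments completed | Status under the stated formula |
|---|---|---|
| 5 of 5 | 0 of 2 | full attendance |
| 1 of 5 | 0 of 2 | partial attendance |
| 0 of 5 | 2 of 2 | neither |

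The statistic can err in either direction. The Section 6.1 grid marks the row for sessions and fidelity at Days 42 and 132, but Sections 6.2.3 and 6.2.4 list only the fidelity form on those days, with no session. The grid therefore does not extend attendance to the assessments.

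**4. Other places where loss is recorded.** Sections 5.2 and 9.2 have a checklist of compliance with data collection. Section 7.2 has retention and dropouts reported to the safety monitor. Section 9.2 (Aim 2b) compares participant characteristics. Sections 10.2.3 and 10.2.5 track missing items and missing hair samples. None of these defines a retention rate at Day 42 or Day 132, and none settles which follow-up rule applies.

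**5. Illustration for a later trial (assumed; the documents give no dropout rate).** Suppose everyone attends at least one session and 5–20% miss Day 132. The proportion with full or partial attendance is 100%, and completion is 95–80%. Recruitment inflation is 1/0.95 = 1.05 to 1/0.80 = 1.25. A planner who took the session-based figure as completion would use 1/1.00 = 1.00.

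**6. Context: the plan's own power figure.** Section 9.1 states 80% power for an effect size of 0.30 with 116 families, intra-family correlation 0.10 and alpha 0.05 (two-sided assumed here). With λ = J·ES²/(4·(ICC + (1 − ICC)/m)) and m = 4 adults per family, λ = 116 × 0.09/(4 × (0.10 + 0.90/4)) = 10.44/1.30 = 8.03. The noncentral F with 1 and 114 degrees of freedom gives 80.2%. So 80% is reached at the top of the stated range of 2–4 adults, with no allowance for loss. Assumed individual losses of 10%, 20% and 30% at the endpoint (m = 3.6, 3.2 and 2.8) give 77.3%, 73.7% and 69.4%. These use endpoint data only, so they ignore what the model recovers from earlier assessments. The session-based rate need not change in any of these cases. The point does not depend on this calculation.

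**The case against.** - **The two sections can be read in sequence.** Staff ask under Section 8 and stop under Section 4.3 if the person declines. This is reasonable as an intention, but Section 4.3 contains no asking step. Its trigger is the decision to end participation, and Section 8 expressly covers that decision. The Section 4.3 sentence about following all families does not help, because the next sentence makes the individual exception.
- **The attendance sentence speaks of proportions in the plural.** It may mean that full and partial attendance are reported separately, with no yes/no retention status. That reading is fair, and it weakens any single figure of 100%. Two attendance proportions still say nothing about Day 42 or Day 132.
- **The inflation figures rest on assumption.** This stands. They assume that a planner would take session attendance as the completion rate. The plan names effect sizes, standard deviations and correlations as what informs the next trial. The figures are an illustration, and the conclusion does not use them.
- **The information is not lost.** This also stands: completion could be counted from the checklists and monitoring reports. The defect is that the rate named in Aim 2a is defined as something else.
- **The group affected by the follow-up conflict may be small.** Section 4.3 anticipates low attrition. The consent form, whose withdrawal terms matter here, was not available for this check.

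**Conclusion.** Both parts hold, and each stands without the other. Sections 4.3 and 8 give incompatible instructions for people who leave the study but would accept assessment. For such a person, the choice of rule decides whether a Day 132 outcome can exist at all. This is a possible loss of endpoint data, not a demonstrated bias, and its size cannot be estimated without a dropout rate.

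The retention formula in Sections 5.2 and 9.2 gives the wrong statistic for a named Aim 2a output. That conclusion needs only the visit schedule and the wording of the formula. Neither problem invalidates the trial, but both should be corrected.

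**What to change.** 1. Reconcile Sections 4.3 and 8 so that one rule on collecting outcome data applies to people who leave the study. For the analysis, permission-based outcome follow-up as in Section 8, subject to the terms of the consent form, preserves endpoint data.
2. In Sections 5.2 and 9.2 (Aim 2a), define retention as the proportion, by arm, completing the Day 42 assessment and, separately, the Day 132 assessment. Report session attendance as its own rate.
3. State the denominator. Families are randomized, so enrolled adults in randomized families is the natural choice. Say whether adults whose data are left out of the main analysis (PHQ-9 of 15 or above, or a diagnosed mental health problem) are counted.

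The cost is wording in Sections 4.3, 5.2 and 9.2, plus the usual review of an amendment by the IRB (Section 11.1) and the safety monitor (Section 7.2). No new data are needed: Section 8 already requires the contact, and the checklists already record compliance with data collection. The reported retention rate may look less favourable.
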